In 1999, the Anderson Orthopaedic Research Institute (AORI) initiated a prospective, Institutional Review Board-approved study to compare the clinical outcome of total hip arthroplasty (THA) patients who were randomized to either crosslinked Marathon or non-crosslinked Enduron polyethylene liners. During an 18-month enrollment period, 226 patients who received 236 THAs consented to participate in the study. Six patients (6 THAs) were excluded intra-operatively, leaving 230 THAs implanted with a Duraloc acetabular shell (DePuy) coupled with a 28-mm cobalt-chrome femoral head (DePuy). At 5-year outcome, we found that crosslinked Marathon polyethylene liners were wearing 95% less than the non-crosslinked Enduron liners [1]. In fact, the Marathon wear rates were so low at 5-year follow-up that the mean was not statistically different than zero. Several other institutions have also reported very low wear rates with highly crosslinked polyethylene based on early clinical outcome data [2-8]. However, since osteolysis typically appears after 5-year follow-up, the reduction in the incidence and extent of periprosthetic bone loss among THA patients with Marathon liners, compared to those with Enduron liners, was not as dramatic as the wear reduction [9]. Despite the substantial reduction in wear that we observed at 5-year follow-up, the patients' perceptions of their outcomes remained similar among the Marathon and Enduron groups [1]. At an average follow-up interval of at least 10-years (using outcome data for individual study participants obtained at a minimum of 9-year follow-up), we anticipated that the reduction in wear associated with Marathon polyethylene would be associated with significant reductions in periprosthetic osteolysis. Our findings [10] confirmed this hypothesis and indicated that the wear rate of Marathon polyethylene remained substantially lower than conventional Enduron polyethylene through 10-year follow-up.

Because crosslinking is accompanied by a reduction in the ultimate tensile strength, fatigue strength, and elongation to failure of ultra high molecular weight polyethylene [11-13], characterizing the long-term clinical performance of Marathon polyethylene is also important. Concerns have been expressed about the potential for the liner fracture, *in vivo* polyethylene oxidation or accelerated wear at long-term follow-up, the effects of femoral head roughening over time and the bioreactivity of crosslinked polyethylene debris particles [14-23]. Ultimately, the best way to address these concerns is in the context of well-controlled, long-term clinical outcome studies. As part of our efforts to follow patients throughout their lives to obtain long-term outcome data, we will continue to obtain routine follow-up at 5-year intervals from the date of surgery for each patient. Because we anticipate that the reduced incidence of wear and osteolysis will result in a lower incidence of revision surgery among the patients randomized to Marathon liners, implant revision for reasons related to wear will be our primary outcome measure at long-term follow-up.

Primary Hypothesis:

- Primary THAs prospectively randomized to Marathon liners will demonstrate a lower rate of revision for wear-related complications and higher survivorship compared to primary THAs randomized to Enduron liners.

Additional Hypotheses:

- Primary THAs prospectively randomized to Marathon liners will demonstrate substantially reduced polyethylene wear compared to primary THAs randomized to Enduron liners.
- THAs prospectively randomized to Marathon liners will demonstrate a reduced incidence of clinically important osteolysis with an area of at least 1.5 square centimeters compared to primary THAs prospectively randomized to Enduron liners.
- THAs prospectively randomized to Marathon liners will demonstrate higher rates of patient satisfaction and better Harris Hip Scores compared to primary THAs randomized to Enduron liners.
- All the THAs prospectively randomized to Marathon and Enduron liners will demonstrate constant wear rates over time.

Study Population

Inclusion criteria

- Patient consented to participate in this study
- Implanted on the acetabular side with a Duraloc 100 cup incorporating a 4-mm lateralized polyethylene liner that was randomized to either Marathon or Enduron
- Implanted on the femoral side with an extensively porous-coated (AML/Solution or Prodigy) stem with a 28-mm cobalt-chrome femoral head

Exclusion criteria

- Intra-operative considerations related to implant stability, leg length correction or bone quality led to the implantation of THA components other than a Duraloc 100 cup, 4-mm lateralized liner, extensively porous-coated stem and 28-mm cobalt-chrome femoral head
- Patient refused reconsent for continued follow-up

Anticipated Study Population Size

The 230 THAs randomized to a Marathon or Enduron polyethylene liner will comprise the study population for our survivorship analyses. Based on our previously published data, we found 9 THAs among deceased patients at a mean follow-up of 5.7 years [1] and 32 THAs among deceased patients at a mean follow-up of 10 years [10]. Based on this data, we anticipate that approximately 12% of the patients enrolled in the study will pass away every five years.

Material and Methods:

- Patients due for routine 15-year follow-up will be contacted by Anderson Orthopaedic Institute personnel who will schedule follow-up appointments. Attempts will be made to obtain follow-up for all enrolled patients who have not had a follow-up evaluation at the Anderson Clinic within one year before the 15-year anniversary of their original surgery date. This procedure will be repeated at five-year intervals (20 years, 25 years, etc.).

Study interval	Minimum follow-up date for study interval	End date
15-year	DOS + 14 years	DOS + 19 years -1 day
20-year	DOS + 19 years	DOS + 24 years -1 day
25-year	DOS + 24 years, etc.	DOS + 29 years -1 day, etc.
Continue every 5 years		

- At the initial follow-up visit associated with this long-term study, the subjects will be informed of changes to the protocol and asked to sign a reconsent.
- At the time of each follow-up visit, patients will complete the clinic patient questionnaire per current protocols and the physician will complete a standardized evaluation.
- Standardized x-rays will be obtained during follow-up visits per current standard of care.
- Subjects who have already come to the clinic for a routine follow-up visit within one year preceding each 5-year anniversary and have not yet signed a reconsent for this long-term follow-up study will be sent a copy of the reconsent in the mail. Designated research personnel will call the subject to review the consent when the subject is able to read along, answer any questions, and ask the subject to send back the signed form if the subject is willing to reconsent.
- Subjects unable to return to the Anderson Clinic for follow-up will be asked to complete the clinic patient questionnaire and a prescription for x-rays will be sent to them after a reconsent has been obtained by telephone as outlined above.
- If a subject does not request to be withdrawn from this study but a fully executed reconsent cannot be obtained (potentially because the subject cannot be contacted), a waiver of informed consent and HIPAA Authorization is requested from the IRB to use the subject's existing medical records for the purposes of this study.
- Serial anteroposterior (AP) pelvic x-rays will be analyzed to evaluate femoral head penetration into the polyethylene liner for each THA using a computer-assisted, validated software application (Hip Analysis Suite, Chicago, IL) [24]. A least-

squares linear regression analysis based on the head penetration versus time in situ will be used to calculate a wear rate for each THA [25]. The Hip Analysis Suite software will also be used to calculate the volumetric wear of the polyethylene liner based on the femoral head penetration data. Wear rates among the Marathon and Enduron groups will be compared using an Independent samples t-test or Mann-Whitney U, depending on the normality of the data.

- Serial x-rays for each THA will be analyzed to identify regions of femoral and acetabular osteolysis. The area of each osteolytic region will be measured on the AP pelvic x-ray with Martell's Hip Analysis Suite software. The incidence of osteolysis will be compared using a chi-square or Fisher's Exact test, depending on the cell counts. The size of osteolytic lesions will be compared using an Independent samples t-test or Mann-Whitney U, depending on the normality of the data. X-rays will also be used to evaluate radiographic complications such as periprosthetic fracture and implant loosening. The incidence of radiographic complications among the Marathon and Enduron groups will be compared using a chi-square or Fisher's Exact test, depending on the cell counts.
- Kaplan-Meier survivorship analysis will be used to compare the outcome of the Marathon and Enduron groups using revision for any reason as an endpoint. Survivorship analyses using revision for specific diagnoses, such as wear and osteolysis or implant loosening, will also be performed.
- Clinical outcome data among the Marathon and Enduron groups will be queried from AORI's institutional database and compared based on the nature and distribution of the data. Specifically, we anticipate that patient satisfaction will be compared with a Fisher's Exact test and Harris Hip scores will be compared with the use of a Mann-Whitney U.
- A manuscript summarizing the results of this study will be submitted for publication in a peer-reviewed orthopaedic journal. The results of this study will also be presented at orthopaedic meetings and conferences.
- Subjects will continue to be followed for life.

Source of Funding

Partial funding for this study will be provided by DePuy Orthopaedics. Study costs in excess of the funding provided by DePuy will be supported internally by the Anderson Orthopaedic Research Institute.

References

1. Engh CA Jr, Stepniewski AS, Ginn SD, Beykirch SE, Sychterz-Terefenko CJ, Hopper RH Jr, Engh CA. A randomized prospective evaluation of outcomes after total hip arthroplasty using cross-linked marathon and non-cross-linked Enduron polyethylene liners. *J Arthroplasty*. 2006 Sep;21(6 Suppl 2):17-25.

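### Minor: ten patients enrolled with two study hips, and the per-hip analyses treat all hips as independent; the effect is small and cheap to remove

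*Combined protocol and SAP*

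**What the plan says.** The opening background gives the counts: "226 patients who received 236 THAs consented to participate in the study", and then "Six patients (6 THAs) were excluded intra-operatively, leaving 230 THAs". Under Anticipated Study Population Size, the analysis population is counted in hips: "The 230 THAs randomized to a Marathon or Enduron polyethylene liner will comprise the study population for our survivorship analyses".

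Material and Methods calculates a wear rate for each THA and compares the groups by independent-samples t-test or Mann-Whitney U. Osteolysis is read from the serial films of each THA and its incidence compared by chi-square or Fisher's exact test. Revision is compared by Kaplan-Meier survivorship, with no named test. Bilateral patients, within-patient correlation and a rule for choosing one hip are not mentioned.

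The wording on what was randomised varies. The background speaks of "patients who were randomized to either crosslinked Marathon or non-crosslinked Enduron polyethylene liners", and the rationale expects a "lower incidence of revision surgery among the patients randomized to Marathon liners". The Primary Hypothesis begins "Primary THAs prospectively randomized to Marathon liners will demonstrate a lower rate of revision for wear-related complications", and the inclusion criteria refer to a "4-mm lateralized polyethylene liner that was randomized to either Marathon or Enduron".

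**The concern.** Two hips in one patient share body weight, activity, bone biology and length of follow-up, so their outcomes are likely to be correlated. Tests that assume independent observations then use a slightly wrong standard error. If both hips received the same liner type, the true variance of the group difference is larger than the test assumes, and the test is too liberal. If the hips were split between liner types, the true variance is smaller and the test is too conservative. The estimated difference itself is not biased by this.

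At stake are the error rate of the wear and osteolysis comparisons and of the revision comparison, which the rationale names as the primary outcome. Follow-up is for life with five-year study intervals, so a rule set now would serve every later report.

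**Working it through.** **Counts.** The plan's own figure reproduces: 236 − 6 = 230 THAs. Patients with two study hips at enrolment: 236 − 226 = 10.
- Plain reading, six patients with one study hip each leave: 226 − 6 = 220 patients, of whom 210 have one hip and 10 have two; 210 + 20 = 230.
- Lower bound, all six excluded hips came from bilateral patients who stayed in for the other hip: 10 − 6 = 4 pairs; 222 + 8 = 230.

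Ten pairs are 20 of 230 THAs (8.7%); four pairs are 8 of 230 (3.5%). These shares persist over follow-up if bilateral patients die at the same rate as others.

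**Assumptions not in the documents.** Two-sided 5% level, 115 THAs per arm, within-patient correlation ρ of 0.5 to 1 (1 is a limiting case).

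**Variance factor.** Each same-arm pair adds 2ρσ²/115² to the variance of the mean difference, and each split pair subtracts the same amount. Relative to 2σ²/115:

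f = 1 + 2ρ(same-arm pairs − split pairs)/230

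Actual type I error = 2[1 − Φ(1.96/√f)]

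| Pairs | Allocation | ρ | f | Type I error |
|---|---|---|---|---|
| 10 | all same arm | 0.5 | 1 + 10/230 = 1.043 | 5.50% |
| 10 | all same arm | 1 | 1 + 20/230 = 1.087 | 6.01% |
| 10 | all split | 0.5 | 1 − 10/230 = 0.957 | 4.51% |
| 10 | all split | 1 | 1 − 20/230 = 0.913 | 4.03% |
| 4 | all same arm | 0.5 to 1 | 1.017 to 1.035 | 5.20% to 5.40% |
| 4 | all split | 0.5 to 1 | 0.983 to 0.965 | 4.80% to 4.60% |

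If hips were randomised independently, the number of same-arm pairs is binomial(10, 0.5) and type I error averages 5.00%. Between 2 and 8 same-arm pairs (probability 0.979) give 4.70% to 5.30% at ρ = 0.5.

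**Which p-values could cross 0.05.** The unadjusted p that corresponds to a correct p of 0.05 is 2[1 − Φ(1.96√f)]. This is 0.045 (same arm) or 0.055 (split) at ρ = 0.5, and 0.041 or 0.061 at ρ = 1.

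**Simulation, wear** (normal data, no true difference, ten pairs, 40,000 runs per cell, Monte Carlo error 0.11 points). The ordinary t-test rejected in 5.46% and 5.91% of runs with same-arm pairs (ρ 0.5 and 1), and in 4.59% and 3.96% with split pairs. With patient-clustered variance the rate was 4.85% to 5.08% under every allocation.

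**Simulation, osteolysis** (assumed 20% incidence in both arms, 40,000 runs per cell). Chi-square gave 5.57% and 6.14% same-arm, and 4.69% and 4.15% split. Fisher's exact test stayed between 2.75% and 4.37%. Chi-square on one THA per patient gave 4.95% to 5.20%.

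**Simulation, revision** (log-rank, assumed because the plan names no test). The result depends on the assumed correlation.
- Weak dependence: a shared gamma frailty of variance 2 implies a within-pair correlation of the revision indicator of about 0.15 at 9% revision and 0.24 at 16%. The size was 5.2% and 5.3% same-arm, and 4.9% and 4.8% split. The closed form agrees for same-arm pairs: 1 + 0.15 × 20/230 = 1.013 gives 5.15%, and 1 + 0.24 × 20/230 = 1.021 gives 5.24%.
- Strong dependence: with identical event times in same-arm pairs, one simulation (20,000 runs, assumed 8% revision by 15 years) gave 5.8%, against 5.15% for fully independent hips. It gave 4.5% for split pairs when about half shared an event time. A separate simulation with identical times gave about 6.3% same-arm and 4.7% split.

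**The case against.** The best defence is that nothing of consequence follows. Under independent hip allocation the error rate averages 5.0%. The 5.5% to 6.0% range needs all ten pairs in the same arm and a correlation of at least 0.5, and the documents establish neither. Fisher's exact test, one of the two allowed for osteolysis, stays below 5%. For wear, the background reports a 95% reduction at five years, so a p-value near 0.05 is unlikely. All of this stands, and it is why the point is minor. It does not supply a method for paired hips, and the remedy costs almost nothing.

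Three further readings are tempting but not supported.
- A reader might infer that the tests are too liberal because the background speaks of randomised patients. The hypotheses and inclusion criteria speak of randomised THAs or liners. This may be loose wording, and the allocation details may sit in the original 1999 study documents. The direction of the error is therefore open, and the mixed wording is not shown to be an error in this plan.
- A reader might infer that the revision comparison is immune. That holds only if the within-patient correlation is low.
- A reader might infer from "THAs prospectively randomized to Marathon liners will demonstrate higher rates of patient satisfaction and better Harris Hip Scores" that one patient's answer is entered once per hip and pulls the arms together. The questionnaire is not in the documents, the hypothesis is framed per THA, and nothing shows that this double entry occurs.

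**Conclusion.** The point holds as a minor one. Pairing is certain at enrolment (ten patients, if none had more than two study hips), 4 to 10 pairs remain in the analysed set, and the plan does not allow for them. At the extremes, with ten pairs and ρ = 1, type I error runs from 4.0% to 6.0%; at ρ = 0.5 it runs from 4.5% to 5.5%. The log-rank test for the primary outcome moves by a similar amount under strong within-patient dependence and hardly at all under weak dependence. Only an unadjusted p-value of about 0.041 to 0.061 could lead to a different conclusion; for the log-rank test that window is approximate. The figures rest on about equal arms, a two-sided 5% level and assumed correlations. They do not suggest that the trial's main comparisons are unreliable.

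**What to change.** Add a short paragraph to Material and Methods:

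1. Where wear is compared by t-test, keep the mean difference and base its standard error on patient-clustered variance.
2. For revision, osteolysis and any rank-based comparison, keep the planned tests and add a sensitivity analysis on one THA per patient. Fix the rule in advance: the first implanted hip, or a seeded random draw if both were implanted on the same day.
3. Report the number of same-arm and split pairs alongside, so that a reader can see the direction of any effect.

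The cost is a little extra analysis and no new data. The sensitivity analysis alone drops 4 to 10 of 230 THAs, which widens standard errors by √(230/226) = 1.009 to √(230/220) = 1.022, that is by 0.9% to 2.2%.

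### The hypothesis of constant wear over time has no planned analysis: one straight-line slope per hip assumes constancy and cannot test it

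*Combined protocol and SAP*

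**What the plan says.** The last of the Additional Hypotheses reads: "All the THAs prospectively randomized to Marathon and Enduron liners will demonstrate constant wear rates over time". The background text just before the hypotheses explains the interest. Among the published concerns about crosslinked liners it lists "polyethylene oxidation or accelerated wear at long-term follow-up", and it says that long-term clinical studies are the best way to address such concerns.

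The wear analysis is one bullet in Material and Methods. Head penetration is measured on serial AP pelvic films, and a least-"squares linear regression analysis based on the head penetration versus time in situ will be used to calculate a wear rate for each THA". Volumetric wear is derived from the same penetration data. Then: "Wear rates among the Marathon and Enduron groups will be compared using an Independent samples t-test or Mann-Whitney U", depending on normality.

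Films continue to accrue. On follow-up: "This procedure will be repeated at five-year intervals (20 years, 25 years, etc"; on imaging: "Standardized x-rays will be obtained during follow-up visits per current standard of care".

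Nothing in the document compares wear rates between time intervals, checks linearity, or says how much change would still count as constant.

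**The concern.** A least-squares line summarises each hip by a single rate. That suits the separate hypothesis that Marathon wears less than Enduron. It does not address whether the rate changes with time, because a straight line takes a constant rate as given. Followed as written, the plan reports a slope per hip and a between-arm test, and leaves the constancy hypothesis unanswered.

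What is at stake is limited but specific. This is the hypothesis most directly tied to the late-wear concern that the protocol gives as a reason for long-term follow-up. With no criterion set beforehand, a small or non-significant difference between early and late wear could be reported as constant wear.

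**Working it through.** **Step 1. Match hypotheses to analyses.** The document gives no figure for this hypothesis (no SD, margin, power or sample size), so there is none to reproduce. Setting the sections side by side:

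| Hypothesis | Planned analysis |
|---|---|
| Fewer wear-related revisions (primary) | Kaplan-Meier, including revision for specific diagnoses |
| Reduced wear | Slope per THA; t-test or Mann-Whitney U between arms |
| Less osteolysis | Chi-square or Fisher's exact test |
| Satisfaction, Harris Hip Score | Fisher's exact test, Mann-Whitney U (anticipated) |
| Constant wear over time | None |

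**Step 2. What one slope can show.** Assumed: noise-free films at years 1, 5, 10 and 15; rate *a* up to year 10 and *b* after it. Mean time is 31/4 = 7.75 and the sum of squares of time is 110.75. Penetration at the four films is a, 5a, 10a and 10a + 5b.

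- Weight on *a*: (−6.75×1 − 2.75×5 + 2.25×10 + 7.25×10)/110.75 = 74.5/110.75 = 0.6727.
- Weight on *b*: 7.25×5/110.75 = 36.25/110.75 = 0.3273.

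So slope = 0.6727a + 0.3273b:

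- constant 0.0231: slope 0.0231;
- accelerating, 0.010 then 0.050: 0.00673 + 0.01637 = 0.0231;
- decelerating, 0.0295 then 0.010: 0.01984 + 0.00327 = 0.0231.

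These rates were chosen to coincide, but the result is algebraic: every pair (a, b) on that line gives the same slope. With a year-20 film added and other assumed rates, 0.05 then 0.15 gives 0.103, 0.15 then 0.05 gives 0.097, and constant 0.10 gives 0.100.

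**Step 3. What repeated reports could show.** If the slope is recalculated on films to year 10, 15 and 20, the three hips in Step 2 give:

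| True pattern | To year 10 | To year 15 | To year 20 |
|---|---|---|---|
| Constant | 0.0231 | 0.0231 | 0.0231 |
| Accelerating | 0.0100 | 0.0231 | 0.0311 |
| Decelerating | 0.0295 | 0.0231 | 0.0192 |

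The serial films therefore carry the information, but the comparison that would use it is not in the plan.

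**Step 4. Precision of a direct estimate.** The contrast for one hip is (y15 − 2·y10 + y5)/5, the rate in years 10–15 minus the rate in years 5–10. With film SD *s*, its film-error SD is √6·s/5 = 0.490s.

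Hips per arm: the document counts 32 THAs in deceased patients at 10 years and says "we anticipate that approximately 12% of the patients enrolled in the study will pass away every five years". Applying 12% to 230 THAs gives 27.6, so (230 − 32 − 27.6)/2 = 85 with equal arms (assumed; arm sizes are not given). This removes deaths only. The lower value of 60 is assumed, to allow for missing films and revisions. Film SD (0.10–0.20 mm) and between-hip SD of the true change (0–0.05 mm/y) are also assumed.

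Half-width = 1.96·√((0.490s)² + between-hip SD²)/√n:

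| Film SD | Between-hip SD | n = 85 | n = 60 |
|---|---|---|---|
| 0.10 | 0 | 0.010 | 0.012 |
| 0.10 | 0.05 | 0.015 | 0.018 |
| 0.20 | 0 | 0.021 | 0.025 |
| 0.20 | 0.05 | 0.023 | 0.028 |

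**Step 5. Effect of actual film dates.** The study-interval table lets a 15-year film fall from 14 years to the day before 19 years. For gaps d1 and d2 between three films, the film-error SD is s·√(1/d1² + (1/d1 + 1/d2)² + 1/d2²). Example dates: 5/10/19 gives 0.386s, 5/10/15 gives 0.490s, 5/9/14 gives 0.552s and 5/13/15 gives 0.810s. The table in Step 4 holds only for exact dates.

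**The case against.** The case on the other side is substantial.

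- **The data are kept.** Penetration is measured on serial films for every hip, so constancy can be analysed later without loss. This stands: the gap is in the analysis plan, not in data collection. A reader might infer that the trial cannot detect a change in wear; Step 3 shows that it can.
- **Recalculated slopes would be enough.** A reader might object that they are inferior because early films dilute the change. That does not hold, because the noise shrinks with the signal. The slope on years 1/5/10/15 minus the slope on 1/5/10 has film-error SD 0.125s and weight 0.327 on the true change, which is 0.381s per unit of change. A piecewise fit to the same four films also gives 0.381s, and films at 5/10/15 alone give 0.490s. The objection to relying on recalculated slopes is only that the plan states neither the comparison nor a criterion.
- **Reference 25 may supply the method.** It is cited for the regression, and its title concerns temporal wear patterns and bedding-in. Its content is not available here, and the protocol adopts no test of constancy from it. Nor does the document give a size for bedding-in, so it cannot be claimed that early films distort the result.
- **The illustration uses assumed inputs.** True of the rates, film years, SDs and lower hip count. The identifiability argument in Step 2 does not depend on the particular values; the precision figures do.
- **It is only an additional hypothesis.** True. A reader might infer that the main conclusion is at risk; it is not, because the revision analysis does not use wear slopes.

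**Conclusion.** The point holds. A stated hypothesis has no analysis that could answer it, and the planned slope takes for granted what the hypothesis asserts. Constant, accelerating and decelerating wear can give the same 15-year slope (0.0231 mm/y under the assumed films and rates).

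This should be corrected, but its reach is narrow. The primary revision analysis and the between-arm wear comparison stand as planned, and osteolysis and loosening are analysed separately. The documents do not show that wear changes over time, only that the plan has no stated way to find out.

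The hypothesis is also worded for every hip. With film-error SDs per hip of about 0.39s to 0.81s at the example dates (0.04 to 0.16 mm/y for s of 0.10 to 0.20 mm), these data can support a statement about an arm mean, not a classification of single hips.

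**What to change.** Keep the slope per THA and the between-arm test. Add to the wear bullet in Material and Methods:

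> Within each arm, the mean within-hip change in wear rate (later minus earlier interval, using actual film dates) will be estimated from the serial films by paired interval rates or a piecewise-linear mixed model using all available films, including those of hips later revised or lost. It will be reported with a 95% CI against a margin fixed before analysis; a non-significant change will not be read as constant wear. The numbers of hips revised for wear or lost before the later film will be reported by arm.

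As a sensitivity analysis, repeat the estimate without the earliest films, in case bedding-in affects them. Reword the hypothesis so that it refers to the mean wear rate in each arm. The sponsor has to set the margin, since the document gives nothing from which to derive one.

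Costs: a little extra analysis on films already planned. Precision is limited (Steps 4 and 5), so constancy against a tight margin may not be shown. Hips revised, or whose patients die, before the later film contribute little to the late rate. Using all available films and reporting the losses by arm makes this selection visible, but some bias remains.

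### The osteolysis analysis does not carry over the 1.5 cm² criterion, ignores time at risk, gives no rule for revised hips, and compares lesion size in what reads as a post-randomisation subset

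*Combined protocol and SAP*

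**What the plan says.** All references are to the combined protocol and SAP.

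- **Additional Hypotheses:** Marathon hips are expected to show "reduced incidence of clinically important osteolysis with an area of at least 1.5 square centimeters" relative to Enduron hips.
- **Material and Methods, osteolysis bullet:** serial films of each THA are read for femoral and acetabular lesions, and "The area of each osteolytic region will be measured on the AP pelvic x-ray". Two tests follow: "The incidence of osteolysis will be compared using a chi-square or" Fisher's exact test, according to cell counts, and "The size of osteolytic lesions will be compared using an Independent samples t-test or Mann-Whitney U, depending on the normality of the data". The bullet states no size threshold, time point, denominator or unit of analysis, and no rule for hips whose patients died or that were revised.
- **Material and Methods, interval table:** under the column "Minimum follow-up date for study interval", the 15-year interval opens 14 years after surgery and closes one day short of 19 years.
- **Anticipated Study Population Size:** the 230 randomised THAs are named as the population for the survivorship analyses. About 12% of patients are expected to die every five years.
- **Material and Methods, survivorship bullet:** Kaplan-Meier is planned for revision, including revision for wear and osteolysis. It is not planned for radiographic osteolysis.
- **Opening background paragraphs:** osteolysis is said to appear typically after five years. The 10-year report is described as "using outcome data for individual study participants obtained at a minimum of 9-year follow-up".

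**The concern.** Four things are left open or handled weakly for a named hypothesis.

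1. **Threshold.** The hypothesis is about lesions of at least 1.5 cm², but the test sentence is about osteolysis without qualification. Every area is measured, so either version could be run and reported. If small lesions occur in both arms, counting them dilutes the contrast.
2. **Time at risk.** A test of two proportions treats a hip last filmed at year 14, one filmed near year 19 and one whose patient died at year 7 as equally informative. With randomised arms this need not favour either liner, but the resulting proportion is not an incidence at any stated time.
3. **Revised hips.** The plan expects less wear and osteolysis with Marathon, and therefore fewer revisions. If hips revised before the interval opens were left out, the hips removed would be mainly Enduron hips with osteolysis, and the arms would look more alike than they are.
4. **Lesion size.** Only hips with lesions have a lesion size. If Marathon prevents lesions, the hips that still have them are not comparable between arms. Its remaining lesions could even look larger if it mainly prevented small ones. One hip may also have several femoral and acetabular lesions, which are not independent observations.

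**Working it through.** **The plan's own figure.** The only planning figure that bears on time at risk is the mortality of about 12% per five years. The inputs are 230 THAs, with 9 in deceased patients at a mean of 5.7 years and 32 at a mean of 10 years.

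- Hips in living patients: 230 − 9 = 221 at 5.7 years; 230 − 32 = 198 at 10 years.
- Constant hazard over the 4.3 years between: 1 − (198/221)^(5/4.3) = 12.0%. The figure reproduces.
- Carried forward: 198 × 0.88 ≈ 174 hips in living patients at 15 years, and 198 × 0.88² ≈ 153 at 20 years. Observation time will therefore differ materially between hips.

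The documents give no osteolysis rates and no arm sizes. Everything below is an illustration under assumed rates and, where a sample size is needed, an assumed 115 hips per arm.

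**Threshold.** Assume lesions of at least 1.5 cm² in 20% of Enduron and 5% of Marathon hips. Let a share s of the remaining hips in each arm have only smaller lesions. Counting any lesion gives 0.20 + 0.80s versus 0.05 + 0.95s. Power is for a two-sided 5% test of two proportions (normal approximation).

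| s | Enduron | Marathon | Power |
|---|---|---|---|
| 0 (threshold applied) | 20% | 5% | 94% |
| 0.10 | 28% | 14.5% | 71% |
| 0.20 | 36% | 24% | 51% |
| 0.30 | 44% | 33.5% | 37% |

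**Width of the window.** With a constant hazard and 15-year incidence p, the expected incidence at t years is 1 − (1 − p)^(t/15).

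| p | Film at 14 years | Film at 19 years |
|---|---|---|
| 10% | 9.4% | 12.5% |
| 20% | 18.8% | 24.6% |
| 30% | 28.3% | 36.4% |

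**Deaths, if all hips are in the denominator.** Spread onset evenly over years 5 to 15 and take survival from the plan's death counts, extending the 5.7-to-10-year hazard to year 15. The observed proportion is p × (1/10)∫S(t)dt over years 5 to 15, and the integral term is 0.863. So 30% becomes 0.30 × 0.863 = 25.9%, and 5% becomes 4.3%. The difference falls from 25 to 21.6 points, and the risk ratio stays at 6.

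**Revised hips, only if they are left out.** With incidence I and a share r of the arm's hips revised for osteolysis before the interval, the incidence among the rest is (I − r)/(1 − r). Assume no such revisions with Marathon.

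- Enduron I = 30%, r = 10%: (0.30 − 0.10)/0.90 = 22.2%. Against 5%, the difference goes from 25 to 17 points.
- Enduron I = 40%, r = 5%: 0.35/0.95 = 36.8%. The difference goes from 35 to 32 points.
- Enduron I = 40%, r = 12%: 0.28/0.88 = 31.8%. The difference goes from 35 to 27 points.

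In counts, take 30/115 Enduron versus 10/115 Marathon and remove revised Enduron hips that had osteolysis:

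| Removed | Enduron | Fisher p |
|---|---|---|
| 0 | 30/115 | 0.0008 |
| 5 | 25/110 | 0.005 |
| 10 | 20/105 | 0.031 |
| 15 | 15/100 | 0.20 |
| 20 | 10/95 | 0.81 |

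**Lesion size.** No arithmetic applies. A lesion's size exists only where there is a lesion, and the hypotheses predict that having one depends on the liner. The compared groups are therefore not the randomised groups.

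**The case against.** The strongest reply is that most of this is silence, not decision. The methods never say that any lesion counts. The hypothesis stands, and measuring each area is exactly what the 1.5 cm² criterion needs. No text excludes revised hips: serial films of each THA can include films taken before a revision, and revision for wear and osteolysis has its own survivorship analysis. The interval table follows a bullet on scheduling visits and defines no analysis set, and the 9-year minimum describes an earlier report. The proportion of all hips with observed osteolysis, followed to year 15 or death, is a legitimate quantity: the cumulative incidence with death as a competing event. Nothing suggests that mortality differs by arm. The hypothesis is also not the primary one.

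Much of this stands. A reader might infer that the plan has abandoned its 1.5 cm² endpoint, that it discards hips revised for osteolysis, or that it analyses lesion by lesion. The documents support none of these: the threshold is not carried over, the revised hips have no rule, and the unit is not stated. Nor is the fall from 30% to about 26% evidence of bias.

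What the reply does not remove is the choice of methods. A proportion test is stated and does not use observation time, across a window almost five years wide. The size comparison is stated and naturally excludes lesion-free hips. A minimum follow-up date for each interval, together with the 10-year precedent, makes an analysis of late-followed hips only a realistic possibility that the plan should rule in or out.

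**Conclusion.** The point holds as a weakness in the analysis of an additional hypothesis. The incidence test does not name the criterion it is meant to test and does not account for time at risk. The size test, on its natural reading, is not a comparison of randomised groups. The handling of revised hips is undefined, and the bias would run towards no difference if they were left out.

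The size of the problem depends on assumed rates. Leaving out revised hips could take 3 to 8 points off a difference of 25 to 35 points, assuming 5% to 12% of Enduron hips and no Marathon hips are revised for osteolysis. Even then, a contrast such as 22% versus 5% remains large. Counting small lesions could lower power from 94% to between 71% and 37% if they occur in 10% to 30% of the other hips in both arms. Differences in film date alone could move a 20% incidence between about 19% and 25%. The change should be made, but the point does not touch the primary hypothesis on revision.

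**What to change.** **Incidence.** Define the event as the first film, including films taken before a revision, with osteolysis of at least 1.5 cm², or revision for osteolysis. Analyse time to that event by arm on all randomised THAs, using a method suited to interval-censored data with film dates as the interval limits. Treat death as a competing event, and report the 15-year cumulative incidence by arm. Stating how death is handled matters: in the illustration above it decides whether the Enduron figure is 30% or about 26%.

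**Size.** Compare total osteolytic area per hip, with zero for lesion-free hips, on all hips with films. Use the last film before revision or death. Report follow-up time at that film by arm, or adjust for it, because a zero at an early last film means less than a zero at year 15.

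**Cost.** A change of analysis wording. The films are already to be read serially and the areas measured, so no new data are needed. The price is a somewhat more complex analysis than a 2×2 table. The simple proportions can still be tabulated descriptively, with their denominators stated.
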